#### **Sedation measures:**

- T-SHAS score (total score on Subjective High Assessment Scale)
  - Mean Total-SHAS score at peak PD response (2-3h) at each baclofen dose level, relative to placebo
  - Time-course of T-SHAS at each baclofen dose level, relative to placebo

#### **Symptom measures:**

- Drug Effects Questionnaire (DEQ)
  - Mean ‘Drug liking’ and ‘want more’ scores at peak PD response (2-3h) at each baclofen dose level, relative to placebo
  - Time-course of DEQ scale at each baclofen dose level, relative to placebo

### **3.4.5 Exploratory Outcomes**

#### **Sedation measures:**

- T-SHAS score (total score on Subjective High Assessment Scale)- self-rated
  - Mean Total-SHAS score at peak PD response (2-3h) at 60mg baclofen dose level, relative to historical controls
  - Time-course of T-SHAS at each baclofen dose level, relative to placebo

#### **Plasma levels: PK and growth hormone measures:**

- Plasma baclofen concentrations
  - Mean peak plasma concentration (2-4h) at each baclofen dose level, relative to placebo
  - Time-course of plasma baclofen levels

- $C_{max}$  (maximum (or peak) plasma concentration,  $T_{max}$  (time to reach  $C_{max}$ ),  $t_{1/2}$  (elimination half-life))
  - Variability in PK parameters by gender
- Plasma methadone concentrations
  - Mean plasma concentration (2-4h) at each baclofen dose level, relative to placebo
  - Time-course of plasma methadone levels
- Plasma [growth hormone (GH)], a surrogate marker of GABA-B receptor function.
  - Mean peak plasma concentration (2h) at each baclofen dose level, relative to placebo
  - Mean peak plasma concentration (2h) at the 60mg baclofen dose level, relative to controls
  - Time-course of plasma GH levels
  - Variability in GH profile by gender

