#### **5.4.3 Baclofen or Placebo Dosing & Administration**

The dose recommendation from the model will be administered approximately 1 hour after methadone. The dose levels are 10mg, 30mg, 60mg or 90mg, administered as either 1, 3, 6 or 9 tablets of baclofen respectively, or a matching number of placebo (vitamin D) tablets which are a very close visual match (see section 5.7).

Effects of baclofen or placebo will be monitored for up to 5 hours following dosing at the Clinical Research Facility. Any lasting effects will be monitored at a follow-up telephone call the following day.

Placebo or baclofen tablets will be administered with water by a nurse or study team member under direct supervision. Participants will not be given the chance to scrutinise the contents of the medication pot prior to consumption. This is a single-blind trial, therefore the participants will not be aware of whether they are taking placebo or baclofen tablets.

NB Baclofen reaches peak maximum concentrations approximately 1-2 hours after oral dosing with 60mg ( $C_{max}$ ; 88-102 minutes, (Durant et al., 2018), and has an estimated half-life in plasma of ~3 hours after a single 60mg dose (range = 2.7-3h from 10-90mg baclofen). All testing will therefore be covered by baclofen's pharmacokinetic profile.

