### **5.4.11 Plasma levels – Baclofen, Methadone, Growth Hormone**

Plasma concentrations of baclofen, methadone and growth hormone will be measured from whole blood. Blood samples of up to 10ml will be obtained at baseline and 1, 2, 3, 5 hours after dosing, in total a maximum of 50ml blood.

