#### **5.7.1 Baclofen in licensed indication**

For baclofen, BNF recommended maximum dose is 100mg/d for licensed indication of spasticity. Example SmPCs for generic baclofen can be found here:

Accord UK Ltd (10mg tablets)

<https://www.medicines.org.uk/emc/product/5728/smpc>

Advanz Pharma (10mg tablets)

<https://www.medicines.org.uk/emc/product/11781/smpc>

Mylan (10mg tablets)

<https://www.medicines.org.uk/emc/product/2594/smpc>

Baclofen is the only selective GABA-B agonist licensed for human use. Originally developed as a potential anti-epileptic in the 1920s, it was found to have anti-spastic effects and is currently used for the treatment of spastic movement, especially in instances of spinal cord injury, spastic diplegia, multiple sclerosis, and amyotrophic lateral sclerosis. It is an orally active *g*-aminobutyric acid (GABA) derivative, p-

chlorophenyl-gamma aminobutyric acid. Its primary action as an antispasticity agent is via simulation of GABAB-receptors resulting in depression of monosynaptic and polysynaptic reflex transmission. Baclofen increases K+ conductance resulting in postsynaptic inhibition and reduces Ca2+ influx and the release probability of excitatory transmitters (glutamate and aspartate) causing presynaptic inhibition in the brain and spinal cord (Katzung, 2009). Baclofen also exerts an antinociceptive effect and may act at supraspinal sites producing CNS depression. Baclofen may also modulate dopamine release in the mesocorticolimbic system by targeting neurons in the ventral tegmental area (Cruz et al., 2004).

Over its many years of use, baclofen has proven to be a very safe drug with few side effects. The main adverse effects are somnolence, dizziness, muscle weakness, and headache. Baclofen has good absorption after oral administration (75%), with peak serum concentrations achieved in 2–4 h. It is weakly bound (30%) to plasma proteins, and is eliminated primarily via the kidneys, 85% as the unchanged parent compound, with an estimated elimination half-life of 3-4 hours. The therapeutic serum concentration for spasticity is 0.08 to 0.4 microgram/ml.

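### The 2-4 h baclofen 'peak' outcome and its placebo contrast do not fit the protocol's own peak times and sampling schedule, and sampling to 5 h leaves individual half-life weak

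*Combined protocol and SAP*

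**What the plan says.** Section 3.4.5, under plasma levels, lists for baclofen "Mean peak plasma concentration (2-4h) at each baclofen dose level, relative to placebo". The same list separately names the time-course, Cmax ("maximum (or peak) plasma concentration"), Tmax, t1/2 and variability in PK parameters by gender.

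The protocol gives two accounts of baclofen kinetics:

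- Section 5.4.3, citing the team's earlier study: "Baclofen reaches peak maximum concentrations approximately 1-2 hours after oral dosing with 60mg", with 88-102 minutes in brackets. That figure is labelled Cmax although it is a time. Baclofen also "has an estimated half-life in plasma of ~3 hours after a single 60mg dose", with a range of 2.7-3 h over 10-90 mg.
- Section 5.7.1, on the licensed indication: "with peak serum concentrations achieved in 2–4 h", and "with an estimated elimination half-life of 3-4 hours".

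On sampling, section 5.4.11 says "Blood samples of up to 10ml will be obtained at baseline and 1, 2, 3, 5 hours after dosing". The visit table in section 4.3.2 agrees and shows no plasma sample at 240 min.

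Hypothesis 3b in section 3.2 expects a PK profile comparable with that of healthy controls and of people with alcohol dependence in the earlier study. Section 8.3.4 refers the PK/PD analysis for GABA-B sensitivity to that study's publication, and section 8.3.5 leaves the detail of exploratory analyses to be described elsewhere.

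**The concern.** The window matches the general figure in section 5.7.1, not the team's own figure in section 5.4.3, and the team's study is also the comparator. With the planned samples, a 2-4 h window means the 2 h and 3 h draws. If the peak lies between 1 h and 2 h, one of the two samples that bracket it is excluded. How far the window value then falls below the true peak depends on how fast each person absorbs the drug, so a difference in absorption between groups could be read as a difference in peak exposure.

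The contrast with placebo is empty for this analyte. Placebo participants take vitamin D tablets (section 5.7) and have no study baclofen in plasma.

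Half-life is a related weakness. The last sample is at 5 h, so few points follow the peak, and they cover little more than one half-life. Hypothesis 3b and the comparison by gender both draw on these parameters.

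**Working it through.** **The sampling plan.** Baseline plus 1, 2, 3 and 5 h is 5 samples. At up to 10 ml each, 5 x 10 = 50 ml, which matches the 50 ml maximum in section 5.4.11. Two post-dose samples (2 h and 3 h) fall inside 2-4 h.

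**Model.** The documents give no concentration model. I assume one compartment with first-order absorption, C(t) proportional to exp(-ke t) - exp(-ka t), with ke = ln 2 / 3 = 0.231 per hour (half-life 3 h, section 5.4.3). ka is solved from Tmax = ln(ka/ke)/(ka - ke). Tmax takes the values in section 5.4.3: 1 h, 88 min, 102 min and 2 h.

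Concentrations as a fraction of true Cmax (results use unrounded values):

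| Tmax | ka | 1 h | 2 h | 3 h | 5 h | Mean of 2 h and 3 h | Largest sample |
|---|---|---|---|---|---|---|---|
| 1 h | 2.68 | 1.000 | 0.862 | 0.689 | 0.434 | 0.78 | 1.00 |
| 88 min | 1.51 | 0.950 | 0.963 | 0.811 | 0.521 | 0.89 | 0.96 |
| 102 min | 1.20 | 0.903 | 0.989 | 0.867 | 0.573 | 0.93 | 0.99 |
| 2 h | 0.92 | 0.840 | 1.000 | 0.926 | 0.646 | 0.96 | 1.00 |

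For example, at 88 min (0.963 + 0.811)/2 = 0.887. Over half-lives of 2.7-4 h, covering both sections, the window mean is 0.88-0.94 for a Tmax of 88-102 min. So within the 1-2 h range of section 5.4.3 the window mean moves from 78% to 96% on absorption speed alone, while the largest planned sample stays at 96-100%.

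**Half-life, bias.** In the model the highest planned sample is at 2 h for Tmax 88, 102 and 120 min. Only the 3 h and 5 h samples then follow the observed peak, and the estimate is 2 ln 2 / ln(C3/C5):

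- Tmax 88 min: 3.14 h against a true 3.0 h (+5%).
- Tmax 102 min: 3.35 h (+12%).
- Tmax 2 h: 3.85 h (+28%).
- Tmax 1 h: the observed peak is at 1 h, so the 2, 3 and 5 h samples can be used. Their log-linear slope gives 3.03 h, essentially unbiased.

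**Half-life, precision.** The CV of a slope-based half-life is roughly (residual CV / sqrt(Sxx)) / ke. Sxx is 2.0 for samples at 3 and 5 h, and 4.67 for 2, 3 and 5 h. With an assumed residual CV of 10%, this gives (0.10/1.414)/0.231 = 31% for two points and (0.10/2.16)/0.231 = 20% for three. At 15% the figures are 46% and 30%. In a simulation with 10% error, one participant's two-point estimate ran from about 2.1 h to 6.5-7.4 h (5th to 95th percentile, Tmax 88-102 min).

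**If section 5.7.1 is right instead.** At a Tmax of 3 h the window mean is 0.97 of Cmax, but the 3 h and 5 h slope returns about 9.4 h for a true 3.0 h. The later peak time helps the window and makes half-life unusable.

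**The case against.** Several points on the other side stand.

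- Cmax, Tmax and t1/2 are already listed. Observed Cmax uses the 1 h sample and loses at most about 4% in the model. A reader might infer that the PK outcomes as a whole are biased. The documents do not support that: the shortfall concerns the window outcome, and the half-life weakness is separate.
- The protocol does not simply put the peak at 88-102 min. Section 5.4.3 also says about 1-2 h, which reaches the 2 h sample, and section 5.7.1 says 2-4 h. The finding is a conflict to reconcile.
- Mean peak may denote the average across participants of each person's highest value in the window. In the model that is the 2 h sample, at 96-100% of Cmax for Tmax 88-120 min. At a Tmax of 1 h it is still only 86%, because the 1 h sample is excluded. The text does not say which reading is meant.
- It is tempting to blame the absent 4 h sample. Adding one would lower the window mean to 81-86% at Tmax 88-102 min.
- The documents specify no half-life method, so a participant-by-participant log-linear fit cannot be attributed to the plan. Larger overestimates (3.4-3.7 h, or 4.6 h at a Tmax of 2 h) arise only if the 2 h sample, which is the observed peak in those cases, is put into the slope.
- Hypothesis 3b compares groups. With the expected minimum of 12 participants at 60 mg (section 4.4.2), an individual CV of 20-46% adds about 6-13% to the group mean's error (divide by sqrt(12)), before between-person variation.
- Section 2.8 plans a similar PK-PD protocol to the earlier study, so shared sampling could cancel part of any error. It would not cancel error from differing absorption, and the match of sampling times for PK cannot be confirmed here.

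**Conclusion.** The outcome is wrong as written, on two grounds that need no model: its window conflicts with section 5.4.3 and omits a planned sample at the edge of that section's peak range, and its placebo contrast has no content for plasma baclofen. The size of the shortfall does need a model. Read as an average, the window gives about 78%, 89-93% and 96% of true Cmax at a Tmax of 1 h, 88-102 min and 2 h, against 96-100% for observed Cmax. Individual half-life is imprecise and modestly overestimated: about 3.1-3.4 h for a true 3.0 h at 88-102 min, about 3.9 h at a Tmax of 2 h, and essentially unbiased at 1 h. These sizes rest on the one-compartment form, a 3 h half-life and, for precision, an assumed 10-15% residual error.

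Severity is minor. The outcomes are exploratory, section 8.1 plans no formal testing, and nothing here enters the DLT model or the dose decisions.

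**What to change.** In the protocol, reconcile the peak times and half-lives in sections 3.4.5, 5.4.3 and 5.7.1, and relabel the 88-102 min figure as Tmax.

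In the detailed SAP still to be agreed:

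- Delete the 2-4 h window and the placebo contrast for plasma baclofen only. A placebo comparison remains meaningful for methadone and growth hormone.
- Use observed Cmax over all post-dose samples (1, 2, 3 and 5 h), as already listed, and add AUC0-5h. Dose-normalise both and compare them across dose levels.
- For hypothesis 3b, compute both measures the same way in the historical groups, using only sampling times shared with the earlier study.
- Preferably estimate t1/2 from one mixed-effects model pooled over all baclofen participants. Otherwise report individual t1/2 as descriptive only, and state which samples enter it.

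The cost is wording and modest analysis time. No extra blood sample, visit or participant is needed.

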**Symptom measures:**

- Visual analogue scales for anxiety, craving at each baclofen dose level, relative to placebo
- Sleep measure (LSEQ) at each baclofen dose level relative to placebo
  - Improvement in LSEQ score for 'getting to sleep' and 'quality of sleep' factors, no change in 'awakening following sleep' or behaviour following 'wake' factors.

**Other outcomes:** actigraphy, heart rate, blood pressure, body temperature.

**Phenotypic measures:** demographic (gender, age), clinical (methadone dose), drug & alcohol history, validated questionnaire measures.

These measures will be related to the primary and secondary outcomes to support the validity of the adaptive trial design, estimate variability in the signal across these demographic features, to establish novel relationships or conversely, to control for outlier effects.

**3.4.6 Evaluation window**

The evaluation window for primary and secondary outcome measures will begin at dosing and end at 5 hours post-dose, with the exception of the 'intervention level' (as defined in the DLT definition) which will begin at dosing and continue until the last follow-up phone call. This call will be conducted the following day, and the window will be extended if the participant is experiencing sedation or other symptoms.

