## **2.10 Study Summary**

This study will evaluate the safety of acute baclofen in methadone-maintained individuals with opiate dependence. The goal of the trial is to study the safety of these drugs given in combination using an adaptive, single-blind, placebo-controlled ascending dose design investigating the impact on respiratory, cardiovascular and pharmacokinetic-pharmacodynamic (PK-PD) parameters.

This study will determine the maximum safe dose of baclofen depending on the prescribed dose of methadone. Methadone doses will vary depending on the recruited cohort, but we anticipate an average dose of ~53mg (range 5 to 120mg), based on data from local drug and alcohol services. We are seeking a minimum safe dose of 30mg baclofen in combination with a minimum of 60mg methadone. Findings will be used to inform a subsequent proof-of-concept trial of the efficacy of baclofen. We will investigate each of the four factors of i) safety, ii) dose-response, iii) potential for abuse liability and iv) objective and subjective measures of GABA-B receptor sensitivity, providing clarity on the relationship between these factors. We will include a placebo arm to evaluate the pharmacodynamic effects of baclofen, and to control for expectation effects.

Safety will be established using a Bayesian dose-escalation adaptive model which will be informed by the occurrence of dose-limiting toxicity (DLT) events at increasing doses of baclofen at the following dose levels: 10, 30, 60, 90mg. The evaluation window for all outcomes will begin at dosing and end at 5 hours post-dose, with further follow-up by phone the following day. The DLT of primary concern is respiratory depression, and we consider that the risk increases with the dose of baclofen and methadone-maintenance level. Formally, the objective is to find the combination associated with 15-25% risk of a DLT. The combination-toxicity response will be evaluated using the continual reassessment method (Wheeler et al., 2019), a model-based design for trials that aim to find the maximum tolerated dose, where the baclofen dose recommendation for each given patient with prescribed dose of methadone will be supported by the adaptive Bayesian model. Participants will be randomised (single-blind) to baclofen or placebo in a 3:1 ratio. If allocated to baclofen, participants will be dosed in groups of up to 3, with a maximum sample size of 48 allocated to baclofen, and 16 to placebo.

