### **5.4.15 Discharge**

Participants will be required to remain under supervision for a period of 5 hours after they receive baclofen/placebo, and remain at the research facility until approved for discharge by the study physician. Staff will ensure that any adverse impacts etc have attenuated before the participant leaves. Study staff will remind participants of relevant study contact details, including a 24-hour mobile telephone number for the on-call study doctor.

Where possible, study staff will arrange for a taxi to take the participant home.

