## **5.5 Follow-up**

Following completion of experimental study visits, participants will be telephoned the day after the visit to check for the following:

- adverse events

- complete sleep and restless legs questionnaire- Leeds Sleep Evaluation Questionnaire (LSEQ, (Parrott AC and Hindmarch I. 1980)
- arrange return of questionnaires and actigraph
- If the participant is still sedated during the call, a second follow up will occur later that day or the following day.

The questionnaires can be completed online, or returned along with the actiwatch in a stamped addressed envelope or via the clinical service.

Any incidental findings will be discussed with the individual and appropriate action taken which could include passing information to GP and/or clinical addiction team as required.

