#### **5.8.7 Definition of completion of the study for an individual participant**

The end of the study will be defined as the last telephone contact visit which is 1 day after their study visit for opiate dependent participants. This represents the end of data collection as defined in ethics and regulatory terms, after which, adverse events will not be recorded.

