#### **7.1.1 Potential Risks**

No treatment is withheld from participants in this study and testing will be performed at times convenient to all persons.

Some participants may find the long experimental study day tiring. We will endeavour to take all steps to ensure comfort and provide appropriate rest and sustenance during these procedures.

In our previously completed study (Durant et al 2018) a few of our healthy volunteers and abstinent alcohol dependent individuals reported minor side effects to the 60mg dose of baclofen, primarily dizziness and, nausea. These side effects resolved and all participants were fit to be discharged by end of the study day. The 90mg dose resulted in more pronounced sedation in one healthy volunteer with mild effects still felt the following day so we did not proceed with testing any further healthy participants at this dose. No such effects were seen in the alcohol dependent group and no significant

cardiovascular effects (e.g. blood pressure, heart rate) were observed in either group. The model in this proposal will mitigate risks of giving such high doses if sedation is seen at lower baclofen doses.

We are carefully monitoring for any signs of respiratory depression and such information will be utilised in the model to determine the next safe dose combination. We have enhanced assessments of possible respiratory impairment in our screening protocol so that anyone at risk of respiratory depression is excluded.

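### After 5 hours only intervention level can yield a DLT: other late findings short of level 4 have no stated route into the dose model, and the sections disagree on the window

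*Combined protocol and SAP*

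**What the plan says.** Section 3.4.2 gives five ways to reach a DLT: (1) a situation needing intervention level 4 or more; (2) a NEWS2 total above 4, or a 3 on any one item; (3) a persistent respiratory change (saturation, respiratory rate, or apnoea with desaturation); (4) a GCS under 12; (5) persistent QTc prolongation. Only the first is said to apply at any time. Section 3.4.3 defines level 4 as failure to rouse the patient by touch.

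Section 3.4.6 has primary and secondary measures "begin at dosing and end at 5 hours post-dose, with the exception of the 'intervention level", "which will begin at dosing and continue until the last follow-up phone call". After mentioning the next-day call it adds that "the window will be extended if the participant is experiencing sedation or other symptoms".

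Other sections bear on the same window:

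- 2.10: "The evaluation window for all outcomes will begin at dosing and end at 5 hours post-dose". Telephone follow-up is mentioned, but no component is exempted.
- 8.3.2: escalation rests on review of safety data from the experimental visit.
- 5.4.7: the last ECG is before discharge, at roughly 5-6 h. The visit table in 4.3.2 puts it at 300 minutes.
- 5.4.15: "Participants will be required to remain under supervision for a period of 5 hours after they receive baclofen/placebo". They then stay until the physician approves discharge and adverse effects have settled.
- 5.5: "If the participant is still sedated during the call, a second follow up will occur later that day or the following day".
- 5.8.5 sets follow-up at 1 day for everyone. 5.8.7 ends the individual's study at the last telephone contact, dated 1 day after the visit, "after which, adverse events will not be recorded".

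**The concern.** Section 2.10 names respiratory depression as the DLT of main interest, and the trial is meant to inform outpatient co-prescription with methadone. Yet the respiratory criteria, NEWS2, GCS and QTc all stop counting at 5 h, and these are the measures that site staff, an ambulance crew or an emergency department could document. The criterion that stays open needs someone at the bedside. Section 3.4.7 nevertheless relies on the telephone call to confirm the absence of a DLT defined by intervention level.

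The model takes only DLT or no DLT for each participant. A late event without a route to a DLT is therefore coded as evidence of safety, and it stays in every later update, including the 92.5% all-safe rule. This error runs in one direction: it lowers the counted risk.

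**Working it through.** **Which late findings count.** Reading 3.4.2, 3.4.3 and 3.4.6 together, for a finding after 5 h and before the last call:

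| Finding | Route to a DLT |
|---|---|
| Cannot be roused by touch | Yes, criterion 1, if someone present documents it |
| GCS below 12, rousable | None stated |
| NEWS2 trigger, rousable | None stated |
| Low saturation, low respiratory rate, or apnoea with desaturation, rousable | None stated |
| QTc prolongation | None stated |

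Staying on site past 5 h does not change this table. Section 3.4.2 does not make a serious adverse event a DLT, and no section says how adverse-event records are converted into DLT status. The table would change only if the extension sentence in 3.4.6 reopens all criteria. It follows the sentence about the call and most naturally extends the intervention-level window, but its scope is not stated.

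**The ECG against its own window.** A prolonged QTc is repeated twice at 5-minute intervals and averaged (3.4.2). Starting at 300 minutes, the last repeat is at 300 + 2 × 5 = 310 minutes, after the window has closed. At the 5-6 h in 5.4.7, the first reading can also fall outside.

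**Exposure at 5 h.** The plan gives no figure for this. Assuming mono-exponential decline after the peak, the share of peak left at 5 h is 0.5^((5 − Tmax)/half-life).

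- 5.4.3 (Tmax 88-102 min, that is 1.47-1.70 h; half-life 2.7-3 h): 0.5^(3.53/2.7) = 0.40 to 0.5^(3.30/3) = 0.47.
- 5.7.1 (Tmax 2-4 h; half-life 3-4 h): 0.5^(3/3) = 0.50 to 0.5^(1/4) = 0.84.

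The time to fall to 10% of peak is Tmax + half-life × log2(10): about 10-12 h on the first set and 12-17 h on the second. Methadone has a half-life of about 24 h (5.4.2).

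**Effect on the count.** Let p be the true DLT risk and q the share of DLTs that arise only after 5 h and are not counted. The counted risk is p(1 − q). The documents do not give q, so it is an assumption, shown over 0-50%.

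- True risk 30%: counted as 27%, 24%, 21% and 15% for q = 10%, 20%, 30% and 50%.
- Share needed to bring the counted risk down to the 25% limit, 1 − 0.25/p: 17% for a true 30%, 29% for 35%, 37.5% for 40%.
- Chance of no counted DLT in a group of 3 at a true 30%: 0.70³ = 0.343 with q = 0; 0.76³ = 0.439 with q = 20%; 0.85³ = 0.614 with q = 50%.

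The effect on the model's stopping probabilities cannot be computed, because the documents do not give the priors.

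**The case against.** **Coma.** A reader might infer that even coma documented in hospital would be coded as no DLT. The text does not support that. An unrousable participant before the last call is at level 4, which 3.4.2 counts at any time and 3.4.6 keeps open. It would be lost only if 2.10 or 8.3.2 were taken to govern.

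**Discharge at 5 h.** A reader might also infer that participants simply leave at 5 h. Section 5.4.15 makes that a minimum stay, with physician approval and settled effects required.

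**Other safeguards.** An uncounted event turns 1 of 3 into 0 of 3 and meets the no-DLT condition in 8.3.2, but that section also requires acceptable safety and tolerability. The Dose Setting Committee can overrule the model (4.4.2, 8.3.2), SAE forms go in within 24 hours (10.1.5) and an independent DMC reviews safety (section 12). A late event would therefore probably be seen. None of these, however, changes the DLT value the model uses.

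**Timing of effects.** Residual concentration is not event risk. Methadone peaks 1.8-3.8 h after its own dose, taken 40-60 minutes before baclofen (5.4.2), so about 0.8-3.1 h after baclofen. Peak subjective effect is expected at 2-3 h (3.2). Both lie inside the window. The case in 7.1.1, "more pronounced sedation in one healthy volunteer with mild effects still felt the following day", shows effects that persisted, not respiratory depression of late onset.

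**A 5-hour endpoint by design.** The sponsor could choose to estimate 5-hour risk. But 3.4.6 carries one criterion to the next day, so the endpoint as written is not purely a 5-hour one.

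**Adverse-event recording.** Sections 5.8.7 and 5.8.8 refer to the last telephone contact, which can include a second call. The conflict lies in the 1-day figures, and arises only when the second call falls on the following day.

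**Conclusion.** The point stands in this form. After 5 h, respiratory depression or reduced consciousness short of level 4, and QTc prolongation, have no stated route to a DLT even when documented. The remaining criterion cannot be scored by telephone. Sections 2.10, 3.4.6, 5.4.7 and 8.3.2 do not describe one window, and the follow-up sections do not fully fit the second call.

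The size is unknown because the late share is not given. A true 30% risk would count as 24% if one DLT in five were late, and a late share of about 17% would suffice to reach the 25% limit. If no DLTs arise late, nothing changes. The documents do not show that late DLTs are common; they show substantial exposure at 5 h and one case of sedation with mild effects still felt the next day.

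Two assumptions remain: the extension sentence does not reopen all criteria, and the separate detailed SAP announced in 8.3.2 and 8.3.7, which is not among these documents, contains no adjudication rule. The correction is warranted because the rule feeds the primary model and each escalation decision.

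**What to change.** 1. Reconcile 2.10, 3.4.6, 5.4.7 (with 4.3.2) and 8.3.2 so that they describe one DLT window, with the last ECG and its repeats clearly inside or outside it.
2. State that any existing criterion in 3.4.2, documented by any source (continued on-site observation, ambulance, emergency department) up to the last call actually made, is adjudicated as DLT or no DLT before the model is updated. If it is learned of later, correct the model data.
3. Record attribution at adjudication, so that an event clearly due to on-top drug use at home is not automatically scored as a baclofen DLT.
4. State which criteria the extension sentence in 3.4.6 covers.
5. Align 5.8.5 and 5.8.7 with the second call in 5.5, so that adverse-event recording ends at the last call made.

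The cost is protocol wording and one eCRF field for late DLT status, with its source and attribution. The downside is that late events are observed less completely than those in clinic, need a judgement on cause, and may raise the DLT count slightly. No assessment or element of care changes.
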